3. STUDY POPULATION

3.1. List the number of subjects to be enrolled.

All patients will be recruited from the ophthalmology and visual science department of Khoo Teck Puat Hospital. There will be no restriction on race. Children will be excluded from this study as the surgeons have limited experience operating on children.

The project aims to recruit 32 patients, 16 in each arm of the randomisation, of phacoemulsification alone and phacoemulsification and iStent Implant.

3.2. Criteria for Recruitment

The subjects will be assessed in the clinic to confirm whether they meet the eligibility criteria and may be enrolled.

Subjects will be invited to participate in the study if they are to be listed for phacoemulsification with lens implantation and meet the inclusion criteria. If the subject expresses interest, then the informed consent form will be given to the subject to read.

3.3. Inclusion Criteria

Provide informed consent

Previous diagnosis of PAC or PACG

IOP above 21mmHg at 3 separate visits

On 1 or more hypotensive medications

Pre-operative VA of no better than 6/12

3.4. Exclusion Criteria

Other glaucoma diagnosis: POAG, secondary glaucoma

PAS in the nasal and inferior quadrant

Cloudy cornea

Previous glaucoma surgery

History of trauma

Ocular surface disease

Pre-proliferative or proliferative diabetic retinopathy

Age related macular degeneration with macular scar or macular atrophy

3.5. Withdrawal Criteria

Complication during phacoemulsification including posterior capsular tear or vitreous loss.

Surgeon is unable to insert the iStent during surgery

Patient request to be withdrawn

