2.2. Primary Objectives

To assess the efficacy of the iStent trabecular micro-bypass stent (Glaukos Corporation, Laguna Hills, CA) in combination with cataract surgery in subjects with primary angle closure and mild to moderate primary angle closure glaucoma

2.3. Potential Risks and benefits:

a. End Points – Efficacy

The primary outcome is: unmedicated IOP \leq 21mmHg at 1 year and mean IOP at 1 year.

A secondary outcome measure is medication reduction at 1 year post operation

b. End Points - Safety

Safety measures include best corrected visual acuity, slit lamp observations, complications and adverse events

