3.6. Subject Replacement

There will be no replacement.

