5.1. Summary of Study Design

Briefly describe the study design and indicate, in general terms, how the design will fulfil the intent of the study.

Single centre, randomised prospective trial, the patient and the IOP checking staff will be blinded. Randomised by random envelope shuffle technique.

2 arms: phacoemulsification alone and phacoemulsification and iStent.

16 patients in each arm, 32 patients in total.

The equal allocation 1:1 ratio will help determine which arm is more efficacious. The regular follow up will determine the safety of the iStent device. The randomisation will avoid surgical bias. The blinding of the patient and IOP measuring staff will avoid observational bias.

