6.3. Study Visits and Procedures

Provide a brief outline of the all the study visits, procedures to be done during the study, follow up after the study and discontinuation visit.

a. Screening Visits and Procedures

No formal screening visit.

The patient will be identified in clinic and be invited to participate in the trial.

b. Study Visits and Procedures

Patients who meet the inclusion criteria will be invited to participate in this study. Patient will be randomly assigned to either phacoemulsification alone or phacoemulsification with iStent by random envelope shuffle technique.

After operation the patient will be followed up at day 1, week 1, week 2, month 1, months 3, 6 and 12.

At each visit the patient will have the following tests: Tonometry (IOP check) - Not to be taken by the operating surgeon, to be taken by 2 people, one IOP checker and one reader.

c. Final Study Visit:

Final visit will be at 1 year after surgery.

Patient will be informed of the procedure performed.

They will resume normal follow up in the clinic for their glaucoma.

d. Post Study Follow up and Procedures

At each visit the patient will have the following tests: Tonometry (IOP check) - Not to be taken by the operating surgeon, to be taken by 2 people, one IOP checker and one reader.

As part of their routine assessment they will be examined for evidence of complications related to the operation.

e. Discontinuation Visit and Procedures

Subjects may withdraw voluntarily from participation in the study at any time.

They will be unmasked regarding the procedure performed. They will need to continue to have the same follow up schedule because it is the same standard of care, except that at each visit they will have tonometry taken by the same doctor (instead of a two person technique) in the clinic who will not be blinded to their operation status.

Subjects may also withdraw voluntarily from receiving the study intervention for any reason. If the patient does not have the operation, then they will receive the standard management for their condition which is usually 6 monthly follow up if their condition is stable.

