9. SAFETY MEASUREMENTS

9.1. Definitions

Reporting procedures for:

- Deaths and life threatening events
- other SAEs: Hospitalisation events.
- Other adverse events

Standard procedures for reporting adverse events

Information regarding adverse events (including incidence, duration, seriousness, severity, relationship to treatment and action taken) will be recorded throughout the one year of the study. If adverse events occur, the first concern will be the safety of the study participants.

9.2. Collecting, Recording and Reporting of “Unanticipated Problems Involving Risk to Subjects or Others” – UPIRTSO events to the NHG Domain Specific Review Boards (DSRB)

An adverse event is defined as any untoward medical occurrence in a patient administered a therapeutic treatment and that does not necessarily have a causal relationship with this

treatment. An adverse event (AE) can therefore also be any unfavourable and unintended sign (including an abnormal laboratory finding), symptom, or disease temporally associated with the use of a therapeutic treatment, whether or not related to the therapeutic treatment.

Any adverse event is to be recorded on the appropriate case report form. These will be graded by an Investigator at each site for severity and relationship to study treatment. The severity should be completed using the following definitions as guidelines:

Mild: Awareness of sign or symptom, but easily tolerated.

Moderate: Discomfort enough to cause interference with usual activity.

Severe: Incapacitating with inability to work or do usual activity.

Not applicable: In some cases, an adverse event may be an 'all or nothing' finding which cannot be graded.

To determine the relationship (if any) between an adverse event and the study drug a causal relationship is deemed present if a determination is made that there is a reasonable possibility that the adverse event may have been caused by the drug.

All adverse events that are therapy related and unexpected should also be reported to the Institutional Review Board.

Procedure for reporting Serious Adverse Events

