9.6. Potential Risks

The potential risks to the patient specific to the iStent are:

The iStent has risks of IOP spikes, infection, bleeding in the anterior chamber and iStent dislocation.

The potential risks to the patient specific to the phacoemulsification are:

Infection, bleeding, reduced vision, inflammation, posterior capsular rupture, vitreous loss, retinal detachment, endophthalmitis, suprachoroidal haemorrhage and IOL dislocation.

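### Section 3.5 withdraws randomised patients for a surgical complication or a failed stent insertion, and the protocol does not say that their one-year safety data are kept

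*Protocol*

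**What the plan says.** Section 3.5 of the protocol lists three withdrawal criteria. One is the patient's own request. The other two are results of the operation: "Complication during phacoemulsification including posterior capsular tear or vitreous loss" and "Surgeon is unable to insert the iStent during surgery". Section 3.6 adds "There will be no replacement".

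Section 2.3b defines the safety endpoints: "Safety measures include best corrected visual acuity, slit lamp observations, complications and adverse events". Section 9.6 names among the risks of phacoemulsification "posterior capsular rupture, vitreous loss, retinal detachment, endophthalmitis", so its first two items are the two events that section 3.5 gives as examples. Section 5.1 explains how the design is meant to establish safety: "The regular follow up will determine the safety of the iStent device".

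Two further places bear on what happens after withdrawal. Section 6.3e says that patients who leave by their own choice are unmasked and "continue to have the same follow up schedule because it is the same standard of care", with pressure then measured by one unblinded doctor. Section 9.1 says that adverse event information "will be recorded throughout the one year of the study". Neither mentions a patient withdrawn because of what happened in theatre.

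**The concern.** A safety outcome of the trial decides who is withdrawn from it. Sections 4 and 6.3b read as if assignment comes before surgery, so both surgical criteria act after randomisation. If data collection stops or becomes optional at that point, the one-year complication and acuity results rest on operations that went well.

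The effect is not balanced. A phacoemulsification complication can occur in either arm, but a failed insertion can occur only where a stent was attempted. Sections 1 and 1.2 describe this as the first study of the device in angle closure and give lack of space as the reason it had not been used there. The insertion failure rate, and how those eyes fare, are therefore device results that the trial should be able to report.

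**Working it through.** **1. Is there a stated figure to reproduce?** No. The protocol gives no complication rate, no failed-insertion rate and no safety denominator. The check is a comparison of passages, followed by an illustration on assumed rates.

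**2. Does any provision secure the data after a surgical withdrawal?**

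| Provision | What it secures | What it leaves open |
|---|---|---|
| 6.3e | Visits continue | Worded for voluntary withdrawal; the reason given is standard of care; does not say that findings enter the study data |
| 4 | Acuity, slit lamp and fundus examination at each visit | Classed as standard care, so attendance alone does not show that acuity is recorded as study data after withdrawal |
| 9.1 | Adverse events recorded for the year | Does not say whether this continues after withdrawal |
| 9.2 | All serious adverse events go to the review board | Not acuity, not non-serious complications, no denominator |
| 9.3 | Regulator told of serious, unexpected, device-related events | A narrower set again |

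The visits largely exist. What is missing is a statement that their safety findings are kept for these patients.

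**3. How likely is it that the rule is used?** Inputs: 32 patients, 16 per arm (section 3.1). Assumptions: one eye per patient, independent eyes, and a rate p of 2%, 5% or 10% for each event. The chance of at least one event in n eyes is 1 − (1 − p)^n. The two criteria need different n: 32 for a phacoemulsification complication, 16 for a failed insertion.

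| p | Complication, expected (32p) | At least one in 32 | Failed insertion, expected (16p) | At least one in 16 |
|---|---|---|---|---|
| 2% | 0.64 | 1 − 0.98^32 = 48% | 0.32 | 1 − 0.98^16 = 28% |
| 5% | 1.6 | 1 − 0.95^32 = 81% | 0.80 | 1 − 0.95^16 = 56% |
| 10% | 3.2 | 1 − 0.90^32 = 97% | 1.6 | 1 − 0.90^16 = 81% |

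The imbalance follows directly. At 5% for each event, the control arm expects 16 × 0.05 = 0.8 withdrawals. The stent arm expects 16 × 0.05 + 16 × 0.05 = 1.6, counting an eye with both events twice.

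**4. What could one or two eyes do to a reported rate?** This applies only if the withdrawn eyes' data are not kept, and only if those eyes had the event being counted. Exact 95% limits are used; for 0/n the upper limit is 1 − 0.025^(1/n).

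- One eye: 1/16 = 6.3% (0.2% to 30.2%) becomes 0/15 = 0% (upper limit 21.8%).
- Two eyes: 2/16 = 12.5% (1.6% to 38.3%) becomes 0/14 = 0% (upper limit 23.2%).

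Step 3 gives the chance that a withdrawal criterion is met. It does not measure the bias. Step 4 shows what is possible, not what is expected.

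**The case against.** The best reply is that the protocol nowhere removes these patients from safety reporting. Section 9.1 runs for the whole year with no stated exception. Section 9.2 sends every serious event to the review board. The reason section 6.3e gives for continued visits applies equally to a patient withdrawn by the surgeon. The complication itself can be recorded on the day of surgery. The definition of a safety analysis set may also sit in an analysis plan that is not shown.

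Much of this stands. A reader might infer from section 3.5 that the safety results exclude these eyes, that nothing keeps them under follow-up, or that their late events and month-12 acuity are lost. The documents support none of these, since they are silent on whether the data are kept. Nor do they give a figure for how much more harm to expect in these eyes.

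Two things remain. Section 3.5 is a positive rule that withdraws patients because of a safety outcome, which is more than a missing detail. And whether data are collected after withdrawal is settled by the protocol: an analysis plan can define a set, but it cannot supply month-12 findings that were not recorded. The imprecision of any rate from 16 eyes is real, but it does not excuse a selection that could favour one arm.

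**Conclusion.** The point holds as a gap with a direction. Section 3.5 withdraws randomised patients because of a phacoemulsification complication or a failed insertion, and the protocol does not commit to keeping their safety data to one year. The reported safety results could look better than the operations were, and more so in the stent arm because only that arm can have a failed insertion.

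The size of any bias cannot be derived from the documents. On assumed rates of 2% to 10%, it is between about even odds and near certainty that at least one of 32 eyes meets the complication criterion (48% to 97%). It is 28% to 81% likely that at least one of 16 stent eyes meets the insertion criterion. With arms this small, one eye can move a reported rate from 6.3% to zero. This rests on assignment before surgery, one eye per patient and independent events. It should be corrected before the data are collected.

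**What to change.** Amend section 3.5 to separate a departure from the assigned operation from leaving the study, and align 6.3e and 9.1 with it:

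- Neither a phacoemulsification complication nor a failed insertion ends safety data collection. It ends only if the patient withdraws consent.
- Every randomised patient who has surgery stays in the safety set, with complications, adverse events and best corrected acuity recorded to month 12 from the visits already scheduled.
- Section 6.3e says that it covers withdrawals triggered in theatre, and that safety findings at those visits are study data.
- Safety is reported by assigned arm and by operation received. Failed insertion is reported as a device outcome, with all attempted insertions as the denominator.

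This leaves surgical decisions and patient care untouched. The cost is a wording amendment and some extra data entry, since the visits and examinations are already standard care. The downside for the sponsor is a possibly less favourable safety result.

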5. STUDY DESIGN

Single centre, randomised prospective trial, the patient and the IOP checking staff will be blinded. Randomised by random envelope shuffle technique.

1:1 ratio allocation

2 arms: phacoemulsification alone and phacoemulsification and iStent.

16 patients in each arm, 32 patients in total.

The post-operative management is the same for both arms

After operation the patient will be followed up at day 1, week 1, week 2, months 1, 3, 6 and 12.

At each visit the patient will have the following tests: Tonometry (IOP check) - Not to be taken by the operating surgeon, to be taken by 2 people, one IOP checker and one reader.

The target IOP is 18mmHg for patients with PAC or mild PACG. If the IOP rises above 18mmHg in 2 consecutive visits then the original glaucoma medication(s) will be reinstated or as per the clinicians discretion.

IOP at 12 months will be the primary outcome measure. The target pressure will be based on the Asia Pacific Glaucoma Guidelines. For PAC with high IOP and PAS and early PACG, the target will be $>/=20\%$ from base line or 18mmHg whichever is lower. b. The Asia Pacific Glaucoma Guidelines classifies “PAC with High IOP and PAS” to be “glaucoma with moderate 5-year risk for visual loss” and to treat the IOP with a target of $>/=20\%$ or 18mmHg whichever is lower.

The target IOP is 18mmHg for patients with PAC or mild PACG. If the IOP rises above 18mmHg in 2 consecutive visits then the original glaucoma medication(s) will be reinstated or as per the clinicians discretion.

The patient will be masked to the treatment arm given, but the investigators will not be masked.

The procedure will be performed by 2 surgeons: [name] and [name], the follow up visits and monitoring of pressure will be done by the investigation team.

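### Failed iStent insertion is a withdrawal criterion that only the stent arm can meet, and the only post-withdrawal rule, if applied, ends masked IOP measurement for those patients

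*Protocol*

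**What the plan says.** Section 3.5 of the protocol gives three withdrawal criteria: a complication during phacoemulsification, "Surgeon is unable to insert the iStent during surgery", and the patient's own request. Section 3.6 adds: "There will be no replacement". Section 5 describes the design as "2 arms: phacoemulsification alone and phacoemulsification and iStent", with 16 patients per arm.

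The one place that says what happens after withdrawal is section 6.3, item e. It has two routes:

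- The first begins "Subjects may withdraw voluntarily from participation in the study at any time". For these patients: "They will be unmasked regarding the procedure performed". Visits go on: "They will need to continue to have the same follow up schedule because it is the same standard of care". The exception is the measurement, which becomes "tonometry taken by the same doctor (instead of a two person technique) in the clinic who will not be blinded to their operation status".
- The second begins "Subjects may also withdraw voluntarily from receiving the study intervention for any reason" and then covers patients who do not have the operation.

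Sections 6.1 and 8.5 require the IOP measurer and reader to be blinded, and section 5.1 relies on this to avoid observer bias. Section 11.2 compares the groups at 12 months with independent t-tests.

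**The concern.** A stent is attempted only in patients assigned to one, so no control patient can meet the failed-insertion criterion, and it can occur only after assignment. It is a one-arm withdrawal after randomisation, caused by the device under test. (The phacoemulsification-complication criterion differs: either arm can meet it, and nothing in the protocol shows a between-arm bias from it.)

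What is at stake is the masked 12-month IOP of these patients. Someone who had phacoemulsification but no stent, and who did not ask to leave, fits neither route of 6.3e by its wording. If a site uses the first route for want of another, unmasked single-observer readings replace masked two-person readings, and for this reason they do so in the stent arm only. An analysis plan can decide which patients and values to use. It cannot recover a masked reading that was never taken.

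**Working it through.** **Step 1: the plan's own figure.** Inputs from section 11.1: difference 2.6 mmHg, SD 2.4 mmHg, alpha 0.05, power 0.80. Sidedness is not stated; two-sided reproduces the result.

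n per arm = 2 × (1.960 + 0.842)² × 2.4² / 2.6² = 13.4, rounded up to 14. This matches. With the 16 per arm of section 5, two-sided t-test power is 84.2%.

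**Step 2: who can meet the criterion, and what follows.**

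| Question | Stent arm | Control arm |
|---|---|---|
| Can failed insertion occur? | Yes | No |
| Replaced? (3.6) | No | Not applicable |
| Named in 6.3e? | No; both routes refer to voluntary withdrawal | Not applicable |
| If the first route of 6.3e is applied | Same visits, unmasked, one unblinded doctor | Not applicable |

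**Step 3: shift from unmasked readings.** The protocol gives neither the number of failures k nor the error m of an unmasked reading. Assume k = 1 to 3 and m = 0 to 2 mmHg. The stent-arm mean moves by (k/16) × m:

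- m = 0: 0
- k = 1, m = 1: 0.0625 mmHg (2% of 2.6)
- k = 3, m = 2: 0.375 mmHg (14% of 2.6)

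The sign of m is unknown.

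**Step 4: shift if the patients were also left out.** The protocol does not state this, so the step is conditional. Let D be how far the 12-month IOP of failed-insertion eyes lies above that of the other stent-arm eyes; assume 0 to 4 mmHg. The shift is (k/16) × D:

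- D = 0: 0
- k = 1, D = 2: 0.125 mmHg (5%)
- k = 2, D = 2: 0.25 mmHg (10%)
- k = 3, D = 4: 0.75 mmHg (29%)

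I also simulated trials with no true effect and SD 2.4, in which k eyes differing by D stay among the controls and are removed from the stent arm. False positives favouring the stent are 2.5% at D = 0, about 4.2% at k = 2, D = 2, and about 8.5% at k = 3, D = 4. With negative D they fall below 2.5%.

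**Step 5: effect on power of keeping the patients.** Suppose failed-insertion eyes have control-like IOP. The expected difference is then 2.6 × (16 − k)/16. Power is for a two-sided t-test at SD 2.4.

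| k | Difference (mmHg) | Power if kept, fixed SD | Power if kept, extra spread simulated | Power if dropped (16 v 16 − k) |
|---|---|---|---|---|
| 1 | 2.44 | 79.4% | about 78% | 83.0% |
| 2 | 2.28 | 73.7% | about 71% | 81.5% |
| 3 | 2.11 | 67.3% | about 64% | 79.9% |

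The SD of 2.4 is below both source SDs in section 11.1 (3.1 and 3.5). At their pooled value, √((3.1² + 3.5²)/2) = 3.31, power with 16 per arm is about 58% with no failures, and about 52%, 47% and 42% with 1, 2 and 3 failures kept.

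**The case against.** The strongest reply is that the protocol is not silent. Section 3.5 lists failed insertion beside the patient's own request under one heading, so a plain reading sends every withdrawn patient to 6.3e, where visits and pressure readings continue. This largely stands. It is a rule that does not name these patients, not an absence of any rule. But that reading confirms the loss of masking.

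Second, the analysis set may be defined in a statistical analysis plan that is not shown. This stands too. A reader might infer from the word withdrawal that these patients are dropped from the 12-month comparison and that the result is therefore biased towards the stent. The protocol does not say they are dropped, and it gives no data on how their pressures would differ. The figures in step 4 are therefore conditional, and the direction is open.

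Third, failures may be few or none. The protocol expects lens removal to make room for the device (section 1) and gives no failure rate. With k = 0 nothing is lost. Against that, sections 1 and 1.2 say the device has not been used or studied in this disease, and the protocol itself provides for failed insertion.

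**Conclusion.** The point holds in a limited form. Failed insertion is a one-arm, device-related withdrawal after randomisation, without replacement. The only available follow-up rule would end masked measurement for these patients, although the design relies on that masking.

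The harm that follows from the protocol itself is lost masked readings in one arm: 0 to 0.375 mmHg with an assumed 1 to 3 failures and an assumed reading error of 0 to 2 mmHg. If the patients were also left out, which is an assumption, the shift would be 0 to 0.75 mmHg for an assumed D of 0 to 4 mmHg. Size and direction cannot be known from the protocol, and both shifts may be zero. It is worth fixing because the remedy is cheap and unmasked readings cannot be repaired afterwards.

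**What to change.** Amend section 3.5 so that failed insertion does not end trial participation. For these patients:

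- continue masked two-person tonometry to 12 months;
- keep the patient masked where possible;
- analyse in the arm assigned;
- report failed insertion as an outcome.

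Limit the unmasking and single-doctor tonometry in 6.3e to patients who themselves withdraw. State in section 11.1 that the 80% power assumes no failed insertions; it should not be described as allowing for them, since step 5 puts power at 16 per arm below 80% for each k from 1 to 3. Clinical management of a failed insertion is left to the investigators.

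The operational cost is two-person tonometry for a few patients whom 6.3e would already keep on the same visit schedule. The statistical price is a diluted stent estimate, as in step 5; that dilution belongs to the effect of assigning patients to the stent procedure. Holding 80% power at failure shares of 1/16, 2/16 and 3/16, at SD 2.4 and with the extra spread simulated, would take about 17, 20 and 23 to 24 per arm. If no insertion fails, the amendment costs nothing.
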